7.3. Evaluating Adverse Events and Serious Adverse Events

Assessment of Intensity:

The investigator or designee will make an assessment of intensity for each AE and SAE reported during the study and will assign it to one of the following categories:

Mild: An event that is easily tolerated by the subject, causing minimal discomfort

 GlaxoSmithKline	Document Name	207235 Clinical Protocol		
	Type	Version	Document Identifier	Effective Date
	eldo_clinical_doc	3.0; Most-Recent; Effective; CURRENT	090032d580cfa41f	07-Mar-2017 08:35:25
	Reason For Issue	Auto Issue		

and not interfering with everyday activities.

Moderate: An event that is sufficiently discomforting to interfere with normal everyday activities

Severe: An event that prevents normal everyday activities. - An AE that is assessed as severe will not be confused with an SAE. Severity is a category utilized for rating the intensity of an event; and both AEs and SAEs can be assessed as severe.

Note: An event is defined as ‘serious’ when it meets at least one of the pre-defined outcomes as described in the definition of an SAE.

Assessment of Causality:

The investigator is obligated to assess the relationship between study product and the occurrence of each AE/SAE.

A "reasonable possibility" is meant to convey that there are facts/evidence or arguments to suggest a causal relationship, rather than a relationship cannot be ruled out.

The investigator will use clinical judgment to determine the relationship.

Alternative causes, such as natural history of the underlying diseases, concomitant therapy, other risk factors, and the temporal relationship of the event to the study product will be considered and investigated.

The investigator will also consult the Investigator Brochure (IB) and/or Product Information, for marketed products, in the determination of his/her assessment.

For each AE/SAE the investigator **must** document in the medical notes (source document) or CRF that he/she has reviewed the AE/SAE and has provided an assessment of causality.

There may be situations when an SAE has occurred and the investigator has minimal information to include in the initial report to GSK. **However, it is very important that the investigator always make an assessment of causality for every event prior to the initial transmission of the SAE data to GSK.**

The investigator may change his/her opinion of causality in light of follow-up

 GlaxoSmithKline	Document Name	207235 Clinical Protocol		
	Type	Version	Document Identifier	Effective Date
	eldo_clinical_doc	3.0; Most-Recent; Effective; CURRENT	090032d580cfa41f	07-Mar-2017 08:35:25
	Reason For Issue	Auto Issue		

information, amending the SAE data collection tool accordingly.

The causality assessment is one of the criteria used when determining regulatory reporting requirements.

7.4. Reporting Adverse Events and Serious Adverse Events

AE Reporting to GSKCH:

AEs will be recorded in the AE section of the CRF.

Medical conditions recorded by the subject on a diary card or similar document that meet the definition of an AE must also be recorded in the AE section of the CRF, if not previously well-characterized by the investigator in the subject's medical history.

AEs elicited by the investigator in a standard manner at the study visits should also be recorded in the AE section of the CRF. The investigator or designee must ask the subject the following question during each visit including any follow-up visits:

“Have you felt unwell, experienced any symptoms or taken any medication (since your last visit) (today) (since your last dose) (since the last session)?”

The medically qualified investigator should review adverse events in a timely manner; this review should be documented in writing in the source document or in the CRF.

After the study is completed at a given site, and the site has received their study data on Compact Discs (CDs), the electronic data collection tool will be removed from the internet to prevent the entry of new data or changes to existing data.

SAE Reporting to GSKCH:

A paper copy of the SAE form provided in the investigator study master file should be completed as fully as possible.

It is essential to enter the following information:

1. Protocol and subject identifiers
2. Subject's demography
3. Description of events, with diagnosis if available
4. Investigator opinion of relationship to study product
5. Criterion for seriousness.

The following are desirable and are of particular relevance for investigator and

 GlaxoSmithKline	Document Name	207235 Clinical Protocol		
	Type	Version	Document Identifier	Effective Date
	eldo_clinical_doc	3.0; Most-Recent; Effective; CURRENT	090032d580cfa41f	07-Mar-2017 08:35:25
	Reason For Issue	Auto Issue		

GSKCH assessment of the SAE report:

1. Date of onset of AE
2. Date AE stopped, if relevant
3. Study product start date
4. Study product end date if relevant
5. Action taken on study product
6. Outcome if known

The SAE form, completed as fully as possible, and SAE fax cover sheet must be faxed or e-mailed to the appropriate SAE Coordinator as soon as possible, **but not later than 24 hours** after study site personnel learn of the event. The SAE Coordinator should be notified of the situation by telephone or email.

Brazil SAE Coordinator ([name]):

7.5. Follow-up of Adverse Events and Serious Adverse Events

Follow-up of AEs and SAEs:

After the initial report, the investigator is required to proactively follow up with each subject and provide further information on the subject's condition.

All AEs/SAEs will be followed until resolution, until the condition stabilizes, until the event is otherwise explained, or until the subject is lost to follow-up.

The investigator is obligated to perform or arrange for the conduct of supplemental measurements and/or evaluations as may be indicated or as requested by GSK to elucidate as fully as possible the nature and/or causality of the AE or SAE.

Investigators are not obliged to actively seek AEs or SAEs in former subjects.

 GlaxoSmithKline	Document Name	207235 Clinical Protocol		
	Type	Version	Document Identifier	Effective Date
	eldo_clinical_doc	3.0; Most-Recent; Effective; CURRENT	090032d580cfa41f	07-Mar-2017 08:35:25
	Reason For Issue	Auto Issue		

However, if the investigator learns of any SAE, including the death, at any time after a subject has been discharged from the study, and considers the event reasonably related to the investigational product or study participation, the investigator will promptly notify GSKCH.

The investigator will submit any updated AE or SAE data to GSK within the designated reporting time frames.

Regulatory and ethics reporting requirements for SAEs:

The investigator will promptly report all SAEs to GSKCH within the designated reporting timeframes (within 24 hours of learning of the event). GSKCH has a legal responsibility to notify, as appropriate, the local regulatory authority and other regulatory authorities about the safety of a product under clinical investigation. Prompt notification of SAEs by the investigator to GSKCH is essential so that legal obligations and ethical responsibilities towards the safety of subjects are met.

GSKCH will comply with country specific regulatory requirements relating to safety reporting to the regulatory authority, IRB/IEC and investigators.

Investigator safety reports are prepared according to GSKCH policy and are forwarded to investigators as necessary. An investigator safety report is prepared for a SAE(s) that is both attributable to investigational product and unexpected. The purpose of the report is to fulfill specific regulatory and GCP requirements, regarding the product under investigation.

An investigator who receives an investigator safety report describing a SAE(s) or other specific safety information (e.g., summary of listing of SAEs) from GSKCH will file it with the Investigator Brochure (or safety statement) and will notify the IRB or IEC, if appropriate according to local requirements.

7.6. Collection of Pregnancy Information

7.6.1. Time Period for Collecting of Pregnancy Information

Collection of Pregnancy Information:

Pregnancy information will be collected on all pregnancies reported following administration of any investigational product.

Information on pregnancy identified during the screening phase and prior to

 GlaxoSmithKline	Document Name	207235 Clinical Protocol		
	Type	Version	Document Identifier	Effective Date
	eldo_clinical_doc	3.0; Most-Recent; Effective; CURRENT	090032d580cfa41f	07-Mar-2017 08:35:25
	Reason For Issue	Auto Issue		

investigational product administration does not need to be collected.

7.6.2. Action to be Taken if Pregnancy Occurs

Action to be Taken:

The investigator will collect pregnancy information on any subject who becomes pregnant while participating in the study after administration of the investigational product. The investigator will record pregnancy information on the appropriate form and submit it to GSKCH within 2 weeks of learning of the subject becoming pregnant. The subject will be followed to determine the outcome of the pregnancy. Information on the status of the mother and infant / neonate (including concomitant medications taken by the mother during the pregnancy) will be forwarded to GSKCH. Generally, follow-up will be no longer than 6 to 8 weeks following the estimated delivery date. Any termination of the pregnancy will be reported.

While pregnancy itself is not considered to be an AE, any pregnancy complication or elective termination for medical reasons will be recorded as an AE or SAE.

A spontaneous abortion is always considered to be an SAE and will be reported as such. An SAE occurring in association with a pregnancy, brought to the investigator's attention after the subject completed the study and considered by the investigator as possibly related to the investigational product, must be promptly forwarded to GSK.

While the investigator is not obliged to actively seek this information in former study participants, he or she may learn of an SAE through spontaneous reporting.

If the subject becomes pregnant during the study they should be withdrawn from the study and this should be recorded in the appropriate section of the CRF

8. DATA MANAGEMENT

For this study subject data will be entered into an electronic case report form, using a GSKCH validated data system.

8.1. Source Documents/ Data

The source documents (e.g. hospital records, clinical and office charts, laboratory notes, memoranda, subjects' diaries or evaluation checklists, pharmacy dispensing records, recorded data from automated instruments, microfiches, photographic

 GlaxoSmithKline	Document Name	207235 Clinical Protocol		
	Type	Version	Document Identifier	Effective Date
	eldo_clinical_doc	3.0; Most-Recent; Effective; CURRENT	090032d580cfa41f	07-Mar-2017 08:35:25
	Reason For Issue	Auto Issue		

negatives, microfilm or magnetic media, x-rays, subject files and records kept at the pharmacy, at the laboratory and at the medico-technical departments involved in the clinical study) which contain the source of data recorded in the CRF should be specified in the Source Document Designation Form. In some cases the printed CRF can be used as a source document.

Each subject will be assigned and identified by a unique Screening Number. Any reference made to an individual subject within the study must be done using the unique Screening Number.

8.2. Electronic Case Report Form

A CRF is a printed, optical, or electronic document designed to record all of the protocol required information to be reported to the sponsor on each trial subject.

For each subject who has given informed consent/assent and has been screened, CRF must be completed and signed by the Principal Investigator (or authorized designee) to certify that the data are complete and correct.

Management of clinical data will be performed in accordance with applicable GSKCH standards and data cleaning procedures to ensure the integrity of the data e.g. removing errors and inconsistencies in the data.

In order to protect the privacy of subjects, no Personally Identifiable Information (PII) (including the subject's name or initials or birth date (day and month)) is to be recorded in the CRF or as part of the query text.

Adverse events and concomitant medications terms (if applicable) will be coded by the sponsor using MedDRA and an internal validated medication dictionary, GSKDrug.

Subject data will be entered into GSKCH defined CRFs and transmitted electronically to GSKCH in a validated (21 CFR Part 11 compliant) web-based electronic data capture system (InForm™).

All CRF pages should be completed during a subject assessment when the CRF has been designated as the source. Data that is sourced elsewhere should be entered into the CRF in an agreed upon timeframe between the Investigator and Sponsor.

The CRFs (including queries, query responses and audit trails) will be retained by GSKCH. Site data archived compact discs (CD(s)) prepared by a third party will be

 GlaxoSmithKline	Document Name	207235 Clinical Protocol		
	Type	Version	Document Identifier	Effective Date
	eldo_clinical_doc	3.0; Most-Recent; Effective; CURRENT	090032d580cfa41f	07-Mar-2017 08:35:25
	Reason For Issue	Auto Issue		

sent to the investigator to maintain as the investigator copy following the decommissioning of the study.

8.3. Data Handling

Documentation of all data management activities should allow step-by-step retrospective assessment of data quality and study performance. Any changes or corrections to data will be performed in the Electronic Data Capture (EDC) System, and it will include rationale for changes. The EDC system has an audit trail, which will provide a complete record of the changes and corrections endorsed by the Investigator.

Protocol deviations are any changes or discrepancies from the protocol that have not been approved by IRB. Protocol procedures should be fully followed, taking appropriate action to prevent any deviations from protocol. However, in case of intercurrents, it is up to the Investigator to analyze the occurrence, as well as the measures that should be taken for the incident.

Any deviation from the plan of this protocol should be described and justified in the final report and submitted to the IRB

8.3.1. Data Queries

Programmed edit checks will be generated automatically, as the data is being entered into the system. Data Management will also run reports and listings on the CRF data, in addition to the queries already programmed and generated by the system, to raise manual queries as needed for site clarification or correction. The Clinical Dictionary Development and Management Group will raise queries as needed on safety data to code the terms (Adverse Events and Drugs) and report appropriately.

The study monitor at the study site will review the CRFs in accordance with the monitoring plan, and any queries will be generated in the EDC System to the Investigator or designee, enabling the errors to be addressed in parallel with Data Management review. Monitor can also run reports and listings on the CRFs, to raise manual queries as needed for site clarification or correction.

 GlaxoSmithKline	Document Name	207235 Clinical Protocol		
	Type	Version	Document Identifier	Effective Date
	eldo_clinical_doc	3.0; Most-Recent; Effective; CURRENT	090032d580cfa41f	07-Mar-2017 08:35:25
	Reason For Issue	Auto Issue		

9. STATISTICAL CONSIDERATIONS AND DATA ANALYSES

9.1. Sample Size Determination

The primary evaluation will be irritation scores after patch removal for each test product at each assessment

No statistical analyses will be performed in this study. The number of subjects to be assessed (N=30 completing the study) was based on clinical considerations.

9.2. General Considerations

9.2.1. Definition of Analysis Populations

The 'Intent to treat' (ITT) population includes all subjects who are randomised into the study and have skin irritation scores from at least one of the test sites available.

Since this is a study to evaluate safety and tolerability, a separate Per Protocol (PP) analysis will not be performed. Protocol deviations will however be listed for review.

The Safety population includes all subjects who received any of the test products. All safety analyses will be performed using the Safety population.

9.2.2. Exclusion of Data from Analysis

No data will be excluded from any analysis.

9.2.3. Criteria for Evaluation

The primary objective will be to assess the skin irritation potential of the test formulations, based on the irritancy score after patch removal. ~~The study will be considered a success if no irritation is observed which is attributable to the test product at any time point.~~ **The study will be considered a success if no irritation is observed which is attributable to the test product at any time point, or if any observed irritation for the test product is not clinically differentiable from the saline solution**

Safety and tolerability will be evaluated by adverse events assessments.

 GlaxoSmithKline	Document Name	207235 Clinical Protocol		
	Type	Version	Document Identifier	Effective Date
	eldo_clinical_doc	3.0; Most-Recent; Effective; CURRENT	090032d580cfa41f	07-Mar-2017 08:35:25
	Reason For Issue	Auto Issue		

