5.4. Product Assignment

Each subject will have all 4 test products and the negative control applied to their backs (dorsum region). The location for each study product application for each subject will be assigned in accordance with the randomization schedule generated by the Biostatistics Department, GSKCH, prior to the start of the study, using validated internal software.

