6.3 Patch Assessments

Experienced trained assessor (s) will assess all patch sites for the duration of the study according to the scoring scale in Appendix 2. Where ever possible the same experienced trained assessor will perform all skin assessments for a given subject at each time point; 15-30 minutes post patch removal (Visit 3, Day 2) in addition to 24 ± 2 (Visit 4, Day 3) and 48 ± 2 hours (Visit 5, Day 4) post patch removal. Patch sites will be graded using a magnifying glass with a fluorescent daylight lamp. The assessor will be blinded to the treatment allocation.

The results will be presented as individual responses to each test product at each assessment time point.

In any case of a positive reaction a dermatologist will be available to perform secondary assessments and grade the response with any further action as needed. This should occur the same day as the initial assessment performed by the trained assessor.

The intensity of any visual signs of irritation will be recorded by the trained examiner, according to the quantity and grade of the reactions (Appendix 2) according to the skin appearance (Scale 1) and other features indicative of irritation (Scale 2) observed. The trained examiner is responsible for grading the reactions, and the trained examiner's opinion on the interpretation of the results is final.

Any observed response which can be denoted using the irritation criteria summarized in Appendix 2, will not be considered an adverse event. In addition any tape-related irritation will also not be noted as an AE. Only in case of unusual reactions, these reactions and the consequences upon the evaluation of the respective test areas will be documented as AE's.

	Document Name	207235 Clinical Protocol		
	Type	Version	Document Identifier	Effective Date
	eldo_clinical_doc	3.0; Most-Recent; Effective; CURRENT	090032d580cfa41f	07-Mar-2017 08:35:25
	Reason For Issue	Auto Issue		

All responses will be reviewed in context of the grading scale in this protocol (Appendix 2).

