Situations where an untoward medical occurrence did not occur (social and/or convenience admission to a hospital).

Anticipated day-to-day fluctuations of pre-existing disease(s) or condition(s) present or detected at the start of the study that do not worsen.

Any observed response which can be denoted using the irritation criteria summarized in Appendix 2, will not be considered an adverse event. In addition any tape-related irritation will also not be noted as an AE. Only in case of unusual reactions, these reactions and the consequences upon the evaluation of the respective test areas will be documented as AE's.

 GlaxoSmithKline	Document Name	207235 Clinical Protocol		
	Type	Version	Document Identifier	Effective Date
	eldo_clinical_doc	3.0; Most-Recent; Effective; CURRENT	090032d580cfa41f	07-Mar-2017 08:35:25
	Reason For Issue	Auto Issue		

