9.3.2. Primary Analysis(es)

The primary analysis will be based on the irritation scores assessed using the dermal scale described in Scale 1 of Appendix 2. No formal statistical inference will be performed. Summary statistics will be presented by product group for skin irritation scores at 15-30 mins, 24 and 48 hours after patch removal. This will include mean irritation scores (if any subjects have reported/developed irritation) and the number and percentage of subjects recording each category of skin irritation scores.

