### 1.1 Study design

This is an evaluator (single) blind, single site, randomized and intra-subject comparison patch test study to evaluate the cutaneous irritation potential of four experimental daily defense serum formulations, including a saline solution as a negative control.

Subjects will be exposed to 24 hour semi-occlusive patch applications of the test products and negative control. At all study visits, subjects will be asked by a trained technician if there have been any feelings of discomfort since the last visit, and also if any medication has been taken during this period.

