**Table 2: Skin Irritation Scoring System – Dermal Response**

Score	Skin Appearance
0	No evidence of irritation
1	Minimal erythema; barely perceptible
2	Definite erythema; readily visible; or minimal edema; or minimal popular response
3	Erythema and papules
4	Definite edema
5	Erythema, edema, and papules
6	Vesicular eruption
7	Strong reaction spreading beyond test site

Summary statistics will be presented by product group for skin irritation scores at 15-30 mins, 24 and 48 hours after patch removal. Number and percentage of subjects recording each category of skin irritation score will be presented in [Table 14.2.1.1](#). Mean, median, min and max irritation scores will be presented in [Table 14.2.1.2](#).

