## 4 Appendix 1:

### 4.1 List of Tables, Listings and Figures

#### 4.2 Tables

Table Number	Table Title (Population)	Template
14.1.1	Subject Disposition (All Screened Subjects)	Appendix 2
14.1.2.1	Subject Demographics and Baseline Characteristics (Safety Population)	Appendix 2
14.1.2.2	Subject Demographics and Baseline Characteristics (ITT Population)	14.1.2.1
14.2.1.1	Frequency of Dermal Response Score by Visit and Treatment (ITT Population)	Appendix 2
14.2.1.2	Average Dermal Response Score by Visit and Treatment (ITT Population)	Appendix 2
14.2.2.1	Frequency of Superficial Irritation (other effects) Score by Visit and Treatment (ITT Population)	Appendix 2
14.2.2.2	Frequency of Combined Score by Visit and Treatment (ITT Population)	Appendix 2
14.3.1.1	Treatment emergent Adverse Event (Safety Population)	Appendix 2
14.3.1.2	Treatment emergent Adverse Event by Severity (Safety Population)	Appendix 2
14.3.1.3	Treatment emergent Treatment Related Adverse Event (Safety Population)	14.3.1.1
14.3.1.4	Treatment emergent Treatment Related Adverse Event by Severity (Safety Population)	14.3.1.2

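### The SAP plans no by-subject output of irritation scores, so the report cannot show whether serum reactors also reacted to saline when both products have reactors

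*Protocol*

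**What the plan says.** SAP 1.1 describes a "randomized and intra-subject comparison patch test study", and Protocol 5.4 puts all four serums and saline on every subject. Saline is the only comparator. Under Protocol 9.2.3 the study succeeds if no irritation is attributable to the product, "or if any observed irritation for the test product is not clinically differentiable from the saline solution".

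On presentation, Protocol 6.3 states: "The results will be presented as individual responses to each test product at each assessment time point". Appendix 2 adds that where a Scale 2 effect is seen, the score is to be reported both as a number with its letter and as a total. Protocol 9.3.2 also asks for by-product summaries: "Summary statistics will be presented by product group for skin irritation scores at 15-30 mins, 24 and 48 hours after patch removal". Protocol 9.3.3 asks for similar summaries of the other effects and the combined score.

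The SAP delivers the by-product part. It plans four irritation tables (14.2.1.1, 14.2.1.2, 14.2.2.1 and 14.2.2.2), each with one column per product within visit. SAP 4.3 plans six listings: deaths, serious adverse events leading to discontinuation, randomisation, protocol violations, and two of adverse events. SAP section 3 declares no change from protocol version 3.0.

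**The concern.** The design gives each subject their own control, and the planned outputs do not report that pairing. A subject with redness at both the serum and saline sites suggests tape, occlusion or generally reactive skin. A subject with redness only at the serum site is a more natural candidate for a product effect. Someone judging whether irritation is attributable to a serum, or distinguishable from saline, would want to see which pattern occurred. If the planned outputs are all the report contains, its reader cannot check that judgement subject by subject.

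Separately, Protocol 6.3 undertakes to present individual responses, and no SAP output does so, although the SAP declares no departure from the protocol.

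**Working it through.** **Do any planned outputs hold individual scores?**

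- The four irritation tables and their templates give counts, percentages or summary statistics for each product at each visit. None crosses a serum score with the same subject's saline score, and none gives a within-subject difference.
- The six listings in SAP 4.3 hold no Scale 1, Scale 2 or combined score. Listing 16.1.7 gives each subject's site and treatment allocation, but no scores.
- The listings that the SAP mentions for blinded data review (SAP 2.2.2, 2.3.1 and 2.3.2) cover medical history, application and adherence deviations, and concomitant medication.
- The adverse event listings cannot stand in. Protocol 7.1.1 says: "Any observed response which can be denoted using the irritation criteria summarized in Appendix 2, will not be considered an adverse event".

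**What can be recovered from the tables?** The plan has no figure to reproduce here: the target of 30 completers from about 40 randomised rests on clinical considerations, and no reaction rate is given. The reactor counts below are therefore assumptions.

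Take one serum and one visit, with n subjects scored at both sites. Call a Scale 1 score above 0 a reaction. Let a be the serum reactors, b the saline reactors and c the subjects who react at both. The tables give a and b, not c.

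- Range of c: from max(0, a + b − n) to min(a, b)
- Serum-only = a − c
- Saline-only = b − c
- Net excess = (a − c) − (b − c) = a − b, whatever c is

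With n = 40 and a = 5, the lower limit of c is 0 in every row:

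| Serum | Saline | c | Serum-only | Saline-only | Net |
|---|---|---|---|---|---|
| 5/40 | 0/40 | 0 | 5 | 0 | 5 |
| 5/40 | 1/40 | 0 to 1 | 4 to 5 | 0 to 1 | 4 |
| 5/40 | 2/40 | 0 to 2 | 3 to 5 | 0 to 2 | 3 |
| 5/40 | 5/40 | 0 to 5 | 0 to 5 | 0 to 5 | 0 |

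The two ranges in a row move together. At 5 against 5, c = 5 gives 0 serum-only and 0 saline-only, and c = 0 gives 5 and 5. At 5 against 2, the pairs are 3 and 0, 4 and 1, or 5 and 2. The counts are the same at n = 30, because a + b never exceeds 10 and the lower limit of c stays at 0.

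The split is fully known when a or b is 0. It is also known in the trivial case where every subject reacts to one of the two products. With complete data, the difference between the mean scores in Table 14.2.1.2 also equals the mean within-subject difference, so the average contrast is not lost.

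**The case against.** The strongest reply is that the tables already carry most of what the criterion needs. The net excess of reactors is fixed by the two totals, and so is the mean difference. The criterion is a clinical judgement with no counting rule, and nothing in Protocol section 9 promises a paired table. The by-product summaries are what 9.3.2 and 9.3.3 ask for. All of this stands, and it makes the cross-tabulation a useful addition, not a missing commitment.

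A reader might infer that up to 5 serum-only reactors at 5/40 against 5/40 would point to the product. They would not by themselves, because they would come with exactly 5 saline-only reactors, which is equal irritation at the negative control.

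A reader might also infer that the pairing is lost. It is not: scores are recorded for each site and subject and kept in the CRF (Protocol 6.3 and 8.2).

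Nor do missing data add much. The intent-to-treat definition admits a subject with a score from only one site, so an unpaired score is possible. But all five products share one patch and are scored at the same visit, so a missed visit normally loses serum and saline together.

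The tables also cannot show whether the same subject reacted at several visits or to several serums, but the criterion does not mention either.

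Finally, the sentence in Protocol 6.3 sits in the assessment section and does not say by subject. Its natural reading still supports a listing of individual scores, though it does not require serum to be paired with saline.

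**Conclusion.** The point holds as a reporting gap. Protocol 6.3 speaks of individual responses and the SAP plans none. In addition, when both products have reactors at a visit, the planned outputs leave the overlap between serum and saline reactors unknown.

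The size depends on reaction counts that the documents do not give. With complete data it is nil if saline is 0 in every subject. Under the assumed 5/40 against 2/40, the net of 3 is known, with 3 to 5 serum-only and 0 to 2 saline-only reactors. Under 5/40 against 5/40, the net of 0 is known, with 0 to 5 of each.

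The documents do not support saying that the success criterion cannot be judged, or that its outcome would change. What is missing is the subject-level evidence behind the judgement. No sample size or inferential quantity is affected.

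**What to change.** Amend SAP 2.4 and 4.2 to 4.3, in this order:

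1. Add a by-subject listing of irritation scores by product and visit, with the Scale 1 score, any Scale 2 letter and the total. This delivers what Protocol 6.3 and Appendix 2 describe, and readers can do the pairing from it. If only one output is added, it should be this one.
2. For each serum and visit, add a descriptive cross-tabulation of the Scale 1 score against the same subject's saline score. Show the number and percentage above, equal to and below saline, and the number that cannot be paired. Its purpose is to inform the clinical judgement in Protocol 9.2.3.

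Keep the four existing tables and the no-inference approach, and add no new decision rule. The cost is one listing and one table from data already collected, and a slightly longer report. Visits, subjects and assessments are unchanged.
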